### **Composite Angiotensin Receptor-Nepriylsin Inhibition may reduce Central Aortic Stiffness in Heart Failure and Improve Ventricular-Vascular Coupling**

Traditional afterload reduction with peripheral vasodilator drugs reduces peripheral resistance, MAP and wave reflection, but does not reduce  $Z_c$ . If cardiac output increases because of the reduction in peripheral resistance, pulsatile overhead will paradoxically increase because the additional flow must be transferred through  $Z_c$ , which remains high. In addition, even more pulsatile energy will be transmitted to the periphery because of the reduction in wave reflection. Thus, traditional vasodilator drugs reduce MAP, which is often already either normal or low in patients with heart failure, yet increase pulsatile stress on the LV and arterial system.

Angiotensin-converting enzyme (ACE) inhibitors and angiotensin-receptor blockers (ARB) may reduce aortic stiffness by opposing vasoconstrictive, hypertrophic, and profibrotic effects of angiotensin II on the vessel wall. Nepriylsin or neutral endopeptidase (NEP) is an enzyme that inactivates several vasodilatory peptides including the natriuretic peptides that are thought to play a role in the body's defense against hypertension. Data from experimental models suggests that natriuretic peptides may have favorable effects on the aorta. Combined

ACE/NEP inhibition with omapatrilat 80 mg was associated with greater reductions in pulse pressure and  $Z_c$  than enalapril 40 mg in the Conduit Hemodynamics of Omapatrilat International Research Study (CHOIR), but was associated with an unacceptable risk of

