##### Screening epoch

Patients will enter a screening epoch up to 6 weeks, beginning with Baseline (Visit 1) at - 42 to -1 day(s) prior to randomization to assess eligibility requirements and to confirm patients are on stable treatment with guideline-directed therapy for HFrEF, other than ACEis and ARBs.

- Screening/Baseline echocardiography (echo), ECG and safety labs will be obtained.
- Non-invasive arterial hemodynamics assessments will be obtained specifically within the window of study day -7 to -2 prior to randomization on Day 1 (Visit 2) to ensure quality control and to allow for a repeat study on day -1, if necessary.
- Biomarkers [REDACTED] will be obtained on Day 1 (Visit 2), pre-randomization.
- If the patient is currently taking an ACEi, a 36-hour washout is required prior to randomization (Visit 2).
- If the patient is currently taking an ARB, they must discontinue the ARB before initiation of study treatment however, washout is not required.

Note: Baseline for this study includes assessments performed during Screening and through Day 1 (Visit 2) pre-randomization.

Patients can be randomized as soon as screening criteria are met.

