1.1 Study design

This study will use a multicenter, randomized, double-blind, double-dummy, parallel group, active-controlled, forced titration, 12-week design in patients with heart failure and reduced left ventricular ejection fraction (LVEF) $\leq 40\%$. The study duration is a maximum of 30 weeks, including the screening epoch, with 8 scheduled outpatient visits. A total of approximately 432 patients randomized to sacubitril/valsartan or enalapril in a 1:1 ratio is planned with no stratification at approximately 80 centers in the United States.

At the time of randomization, patients will have been on stable treatment with guideline-directed therapy for heart failure with reduced ejection fraction, other than angiotensin converting enzyme inhibitors (ACEi) and angiotensin receptor blockers (ARB), and on an optimal medical regimen to effectively treat co-morbidities such as hypertension, diabetes mellitus and coronary artery disease. All patients will need to meet all other inclusion and none of the exclusion criteria.

Patients will be randomized to either sacubitril/valsartan 24/26 mg bis in diem/twice a day (BID) or enalapril 2.5 mg BID (Dose Level 1), according to the product label(s). Forced titration will occur every 2 weeks to reach the target dose of sacubitril/valsartan 97/103 mg BID or enalapril 10 mg BID (Dose Level 3). Dose level 2 is defined as sacubitril/valsartan 49/51 mg BID or enalapril 5 mg BID. Dose adjustments will only be allowed if indicated per protocol defined safety and tolerability criteria and investigator judgement, or if the investigator believes that adjustment/elimination of concomitant medications is not possible or does not alleviate the side effects of concern. After 12 weeks of double-blind treatment, patients will continue into the 12 week open-label extension.

All patients will need to have a 36-hour washout from study treatment prior to starting the open-label extension to ensure that the blinding of the core study is maintained and to reduce the risk of angioedema. All patients will start open-label treatment on sacubitril/valsartan Dose Level 2, unless they completed double-blind treatment on Dose Level 1. Instead, these patients will enter the open-label extension on sacubitril/valsartan Dose Level 1. Study treatment will be force-titrated every 2 weeks to reach the target dose of sacubitril/valsartan (Dose Level 3).

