2.1 Data analysis general information

 a Novartis-designated Contract Research Organization (CRO) will be performing all analyses outlined in this SAP. SAS[®] version 9.3 (or higher) will be used for all analyses.

Data from all centers that participate in this protocol will be combined, so that an adequate number of patients will be available for analysis.

Unless otherwise specified, for continuous data, the mean, standard deviation, median, first and third quartiles, interquartile range, and minimum and maximum values will be presented. Geometric means and 95% confidence intervals will also be presented for biomarker data. For categorical data, frequencies and percentages will be presented. All statistical tests will be conducted against a two-sided alternative hypothesis, employing a significance level of 0.05.

All data will be provided in listings in addition to summaries described below.

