2.2.1 Subgroup of interest

The following subgroups will be analyzed for the primary objective:

1. Age groups (<65, ≥65 years; and <75, ≥75 years)
2. Baseline ejection fraction categories based on echocardiography (<25%, 25% - <35%, ≥35%)
3. Prior ACEi/ARB exposure groups (never exposed, previously exposed, or currently taking)
4. Prior ACEi/ARB dose groups (low dose, high dose) (e.g., low dose: <10 mg enalapril daily [or equivalent]; high dose: ≥10 mg enalapril daily [or equivalent])

5. Baseline quartiles of aortic characteristic impedance (based on FAS)
6. Baseline estimated glomerular filtration rate (eGFR) categories (<45, 45 - <60, ≥60 ml/min/1.73 m²)
7. Groups defined by quintiles of change from baseline in mean arterial pressure at Week 12 (based on FAS)
8. New York Heart Association (NYHA) classification [best value during the past month prior to screening visit] (I, II, III, IV)
9. Prior heart failure hospitalization (No, Yes)
10. Prior diabetes (No, Yes)
11. Baseline plasma NT-proBNP (pg/mL) categories (≤ median, > median) (based on FAS)

See Section 2.5 for further details on the primary objective.

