2.5.2 Statistical hypothesis, model, and method of analysis

Let μ_j denote the population mean of change from baseline in the aortic characteristic impedance at Week 12 for treatment group j , $j = 0, 1$, where 0 corresponds to enalapril and 1 corresponds to sacubitril/valsartan.

The following null hypothesis (H_0) will be tested against the alternative hypothesis (H_A):

$$H_0: \mu_1 - \mu_0 = 0$$

$$H_A: \mu_1 - \mu_0 \neq 0$$

The primary endpoint will be analyzed by an analysis of covariance (ANCOVA) model with treatment and Z_c baseline as explanatory variables (Mitchell 2002). The least squares means of the two treatment groups, least squares mean difference of the treatment groups, 95% confidence interval for the difference in the two treatment groups, and p-value based on the fitted linear model will be reported. If the p-value is < 0.05 and the least squares mean difference

of the treatment groups favors sacubitril/valsartan, statistical significance in favor of sacubitril/valsartan is shown.

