2.14 Interim analysis

No interim analysis is planned.

3 Sample size calculation

In CHOIR (Mitchell 2002), treatment with Omapatrilat was associated with an approximately ~10% reduction in characteristic impedance at 12 weeks, with little or no change seen amongst enalapril- treated patients. Based on a similar study design and population, and accounting for a dropout rate of 20% from first visit to subsequent follow up and a 10% rate of non-evaluable data, assuming a standard deviation of 80 for the primary efficacy variable and 90% power, a sample size of 432 patients (216 per arm) will be necessary to detect a clinically important change of 30 dyne x sec/cm⁵ between the two treatment groups.

Assuming a significance level of 0.05, a sample size 432 patients would provide 88% power to detect a 25% reduction in the geometric mean of the proportional change from baseline to Week 12 in NT-proBNP for the sacubitril and valsartan treatment group assuming a value of 0.95 for the enalapril group, a value of 0.7125 for the sacubitril and valsartan group (25% reduction), a common standard deviation of 0.85 and a 20% drop-out rate. The difference between the logs for the two treatment groups is therefore assumed to be 0.288.

4 Change to protocol specified analyses

The following changes to protocol specified analyses were made:

- Modified baseline definition as follows:
 - Eliminated requirement that assessment date:time is prior to first dose date:time
 - Clarified how baseline assessments for hemodynamic variables will be identified
- Clarified that tables summarizing demographics and baseline data will be run only on the FAS, and not also on the RS as indicated in the protocol
- Indicated that values of the hemodynamic variable carotid-femoral pulse wave velocity will be negative inverse transformed prior to analysis
- Added separate summaries of prior and concomitant CV, HF, ACEi and ARB medications
- Added the following supportive analyses of the primary endpoint:
 - On-treatment analysis

- Analysis using the “original” aortic characteristic impedance variable
- Analysis using the “alternative” aortic characteristic impedance variable
- Added on-treatment analyses of the secondary endpoints
- Modified the PPS definition to clarify that major protocol deviations will exclude patients from the PPS regardless of the study phase in which they occur
- Added summary of the incidence of hypotension through Week 12

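### The primary ANCOVA leaves out prior ACEi/ARB exposure, a plausible predictor of Zc change that is already collected; adding it would buy a little precision at small cost

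*SAP*

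**What the plan says.** - **Primary model.** SAP 2.5.2: "The primary endpoint will be analyzed by an analysis of covariance (ANCOVA) model with treatment and" baseline Zc. SAP 5.5.1 writes out the same model, and Protocol 9.4.2 agrees.
- **Randomization.** SAP 1.1 plans 1:1 allocation "with no stratification at approximately 80 centers".
- **Timing of baseline Zc.** Protocol 3.1: "Non-invasive arterial hemodynamics assessments will be obtained specifically within the window of study day -7 to -2" before randomization, with a repeat on day -1 if needed. SAP 2.1.1 takes the hemodynamic baseline from the Visit 1 time point.
- **Handling of prior drugs.** Protocol 3.1: "If the patient is currently taking an ACEi, a 36-hour washout is required prior to randomization (Visit 2"). An ARB must be stopped before study treatment but needs no washout.
- **Why prior drugs could matter.** Protocol 1.1: "Angiotensin-converting enzyme (ACE) inhibitors and angiotensin-receptor blockers (ARB) may reduce aortic stiffness by opposing" effects of angiotensin II on the vessel wall.
- **What is already collected.** SAP 2.4.2 classifies exposure at screening in three categories. SAP 2.2.1 uses it as a subgroup factor for the primary objective: "Prior ACEi/ARB exposure groups (never exposed, previously exposed, or currently taking". Prior dose group is a further subgroup factor.
- **What is absent.** None of the supportive analyses in SAP 2.5.4 gives an overall treatment estimate adjusted for exposure.

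**The concern.** Take two patients with the same baseline Zc, one measured while taking an ACEi and one never exposed. The model treats them as identical. If both are assigned to enalapril, the first is largely continuing a drug class and the second is starting one, so their expected changes may differ. Baseline Zc absorbs part of any effect of prior treatment, but not the part that concerns what happens next at the same starting value.

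If exposure does predict change, leaving it out keeps avoidable variation in the residual. With no stratification, the estimate also moves with any chance difference between arms in the share of current users. What is at stake is the width of the confidence interval and robustness to that imbalance.

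**Working it through.** **Inputs from the documents.** Test: "All statistical tests will be conducted against a two-sided alternative hypothesis, employing a significance level of 0.05" (SAP 2.1). From SAP Section 3: "assuming a standard deviation of 80 for the primary efficacy variable and 90% power", a difference of 30 dyne x sec/cm⁵, 20% dropout, 10% non-evaluable data, and 216 patients per arm. The SAP does not say whether SD 80 is the raw SD of change or the residual SD after baseline adjustment. It is used here as the SD before the new factor is added.

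**Assumed inputs, not in the documents.** Partial R² of exposure given baseline Zc, 0.01 to 0.10. Share of current users, 50% to 85%. Difference in Zc change between current users and others at equal baseline Zc, 10 to 30 dyne x sec/cm⁵.

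**1. The plan's own figure.** The t-based calculation needs 151 evaluable patients per arm (150 by the normal approximation). Adding the two losses, 151 / (1 − 0.20 − 0.10) = 151 / 0.70 = 215.7, so 216 per arm and 432 in total. The stated size reproduces. Power at 151 per arm is 90.1%.

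**2. Is baseline Zc on-drug?** SAP 2.1.1 numbers study days with no day 0. Counting back 36 hours from a morning randomization on Day 1 reaches the evening of day -2. Protocol 6.4.1 places trough tonometry between 07:00 and 11:00, so a day -2 study can come before the washout starts. Only the optional day -1 repeat would normally fall inside it. For ARB users no washout applies at all.

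**3. Precision.** Residual SD = 80 × √(1 − R²). Half-width = t × SD × √(2/151). Power is from the noncentral t, with two extra degrees of freedom for the factor.

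| Partial R² (assumed) | Residual SD | Power | 95% CI half-width |
|---|---|---|---|
| Factor not in model | 80.0 | 90.1% | 18.1 |
| 0.01 | 79.6 | 90.4% | 18.0 |
| 0.02 | 79.2 | 90.7% | 17.9 |
| 0.05 | 78.0 | 91.5% | 17.7 |
| 0.10 | 75.9 | 92.8% | 17.2 |

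**4. If the factor predicts nothing.** The two degrees of freedom cost less than 0.01 percentage points of power through the critical value. Chance correlation between factor and treatment raises expected variance by (302 − 4)/(302 − 6) = 298/296 = 1.007, about 0.7%.

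**5. Chance imbalance.** The SD of the between-arm difference in the share p of current users is √(2p(1 − p)/151).

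- p = 0.50: SD 0.0575, so the 95% range is 1.96 × 0.0575 = ±11.3 points.
- p = 0.85: SD 0.0411, so ±8.1 points.

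Multiplying by the assumed difference in change gives the shift in the treatment estimate. The lowest value is 0.081 × 10 = ±0.8 and the highest is 0.113 × 30 = ±3.4. These compare with a target of 30 and a half-width of 18.1. The shift is one component of that interval and does not come on top of it.

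**6. How generous is the top of the R² range?** With two groups, R² = g²p(1 − p)/80², where g is the difference in change. For g of 10 to 30, R² runs from 0.002 (p = 0.85) to 0.035 (p = 0.50), which gives power of 90.2% to 91.1%. An R² of 0.10 at p = 0.50 would need g = 80 × √(0.10/0.25) = 50.6, more than the target treatment difference. The upper rows of the table are therefore optimistic.

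**The case against.** The strongest reply is that nothing here is an error. Protocol and SAP agree on a standard baseline-adjusted ANCOVA, and the planned size delivers its 90% power without the extra factor. The documents report neither the prevalence of prior use nor any association with Zc change. SAP Section 3 points the other way, recalling little or no Zc change on enalapril in the earlier omapatrilat trial. The continuation-versus-initiation argument also describes a treatment-by-exposure interaction. An additive factor does not model that, and the planned subgroup analyses by exposure and dose do address it.

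Much of this stands. Exposure is a plausible predictor only, and every gain above rests on assumed inputs. Two things do not follow, however. Subgroup results do not supply an adjusted overall estimate. And an additive factor still captures the main effect of exposure, whether or not an interaction exists. The enalapril finding may point to a low R², but by its title that trial studied systolic hypertension, not HFrEF, so it does not settle the matter.

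A reader might also infer that the same argument carries over to the NT-proBNP and echocardiographic models. The documents do not support that. Biomarker baselines are drawn on Day 1 before randomization (Protocol 3.1 and 6.4.3), when ACEi users should have completed the washout, so the tonometry-timing argument does not transfer for them. For the echo measures the documents give nothing from which a benefit could be shown or sized.

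**Conclusion.** The point holds as a minor suggestion on efficiency and robustness. The model omits a baseline factor that the plan collects, categorizes and considers relevant enough for subgroup analysis. The timing of baseline tonometry gives a concrete reason why it could predict change at a given baseline Zc.

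The benefit is small: 0.3 to 2.7 percentage points of power for an assumed partial R² of 0.01 to 0.10, with the lower part of that range more realistic, plus removal of an imbalance shift of a few units at most.

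A reader might go further and conclude that the primary comparison is biased, or its p-value invalid, because baseline mixes on-drug and off-drug values. That does not follow. Randomization makes exposure independent of treatment in expectation, so the unadjusted-for-exposure ANCOVA remains a valid test of the stated hypothesis.

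**What to change.** Before unblinding:

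- Add prior ACEi/ARB exposure (never, previously, currently) as a fixed factor to the primary ANCOVA in SAP 2.5.2 and 5.5.1, and to the supportive repeated-measures model in SAP 2.5.4.
- Keep the treatment-plus-baseline model as a named sensitivity analysis.
- State a rule for patients with missing exposure status.
- Record the change in SAP Section 4, because Protocol 9.4.2 specifies the present model.

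No new data are needed. The costs are the two degrees of freedom, the 0.7% of expected variance if the factor is not prognostic, and a primary model that no longer matches the one in the trial the SAP cites for it. If the sponsor prefers to leave the primary model alone, the least that would help is to list the exposure-adjusted ANCOVA among the supportive analyses in SAP 2.5.4.

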2.5.3 Handling of missing values/censoring/discontinuations

If a patient has no Week 12 value, the missing value will not be imputed and the patient will be removed from the analysis.

2.5.4 Supportive analyses

A supportive nonparametric analysis will be performed to examine the consistency of results if the assumption of normality for the distribution of the primary endpoint is not tenable. Graphical methods (e.g., normal probability plot and histogram of residuals) and analytical methods (e.g., Shapiro-Wilk test) will be used to assess the assumption of normality. For this supportive analysis, the primary endpoint will be analyzed using the Wilcoxon rank-sum test. The probability of one treatment being the same or better than the other treatment will be estimated (based on the Wilcoxon rank-sum test) and the associated 95% confidence interval will be reported (Chen and Kianifard, 2000).

The following supportive/sensitivity analyses of the primary endpoint will also be performed:

- An analysis based on the FAS using the same analytical approach as described in Section 2.5.2 where missing values at Week 12 are imputed using the Last Observation Carried Forward (LOCF) procedure (only post-baseline trough values will be carried forward).
- An analysis based on the PPS using the same analytical approach as described in Sections 2.5.2 and 2.5.3.
- Change from baseline in aortic characteristic impedance at Weeks 4 and 12 will be analyzed based on a repeated measures ANCOVA model in which treatment, week, and treatment-by-week interaction will be included as fixed-effect factors and the baseline value as a covariate, with a common unstructured covariance for each treatment group. The primary treatment comparison between sacubitril/valsartan and enalapril will be made at Week 12. The analysis will be performed on all available data in the FAS. The estimated treatment effect with the associated two-sided 95% confidence interval at Week 12 will be provided.
- Subgroup analyses based on the FAS as described in Section 2.2.1.
- An on-treatment analysis based on the FAS using the using the same analytical approach as described in Section 2.5.2.
- Analyses of the “original” and “alternative” aortic characteristic impedance variables based on the FAS using the same analytical approach as described in Section 2.5.2.

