### 9.4.4 Sensitivity analyses

A supportive nonparametric analysis will be performed to examine the consistency of results if the assumption of normality for the distribution of the primary efficacy variable is not tenable. For this supportive analysis, the primary efficacy variable will be analyzed using the Wilcoxon rank-sum test. The probability of one treatment being the same or better than the other treatment will be estimated (based on the Wilcoxon rank-sum test) and the associated 95% confidence interval will be reported (Chen and Kianifard, 2000).

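### The nonparametric check on the primary endpoint is the one named supportive test that drops baseline Zc; a baseline-adjusted rank test should be added beside it (minor)

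*SAP*

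**What the plan says.** SAP 2.5.2 sets the primary model: "The primary endpoint will be analyzed by an analysis of covariance (ANCOVA) model with" treatment and baseline Zc as the explanatory terms. The success rule is attached to that model's p-value.

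SAP 2.5.4 then plans a nonparametric analysis to see whether the result holds up if normality is doubtful: "For this supportive analysis, the primary endpoint will be analyzed using the Wilcoxon rank-sum test". Protocol 9.4.4 has the same test: "the primary efficacy variable will be analyzed using the Wilcoxon rank-sum test". Both add an estimate of the probability that one treatment does at least as well as the other, with a 95% confidence interval by a cited procedure. Neither names a covariate or a stratum, and SAP section 4 (changes to protocol-specified analyses) leaves the test alone.

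The other supportive analyses in SAP 2.5.4 keep baseline Zc. The LOCF, per-protocol, on-treatment and original/alternative Zc analyses follow the 2.5.2 approach, and the repeated-measures model lists the baseline value as a covariate. The subgroup item states no model of its own. SAP 1.1 says randomization is unstratified.

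**The concern.** A check on a distributional assumption is easiest to read when that assumption is the only thing that changes. Here the move from ANCOVA to Wilcoxon also removes the baseline adjustment. If the ANCOVA is significant and the Wilcoxon is not, the reader cannot tell whether non-normality or the lost covariate is responsible. A rank test that keeps the baseline would separate the two and would usually be more powerful. At stake is how clearly a supportive result can be read, not the validity of the primary conclusion.

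**Working it through.** **Inputs from the documents.** Two-sided 0.05 (SAP 2.1: "All statistical tests will be conducted against a two-sided alternative hypothesis, employing a significance level of 0.05"). From SAP section 3: "assuming a standard deviation of 80 for the primary efficacy variable and 90% power"; a between-arm difference of 30 dyne x sec/cm5; losses of 20% and 10% ("accounting for a dropout rate of 20% from first visit to subsequent follow up and a 10% rate of non-evaluable data"); and "a sample size of 432 patients (216 per arm) will be necessary".

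**Assumptions.** The baseline-to-Week 12 correlation ρ is not given; 0.3 to 0.85 is used in the simulations. Baseline and Week 12 variances are taken as equal. SD 80 is read as the SD of change, since the primary variable is the change.

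**Reproducing 432.** n = 2 × (1.960 + 1.282)² × 80² / 30² = 149.4, so 150 per arm; the t-test version gives 150.4, so 151. Then 151 / (1 − 0.20 − 0.10) = 215.7, so 216 per arm and 432 in total, as stated. This is an unadjusted comparison of change; no ρ enters it.

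**Splitting the gap at ρ = 0.5, normal data, 151 per arm.**
- Unadjusted t-test on change: SE = 80 × √(2/151) = 9.21; 30/9.21 − 1.96 = 1.30; power 90.3%.
- Wilcoxon on change, efficiency 3/π: 3.258 × √(3/π) − 1.96 = 1.22; power 89.0%.
- ANCOVA: residual SD = 80 × √((1+ρ)/2) = 69.3; SE = 7.97; 30/7.97 − 1.96 = 1.80; power 96.4%.

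Of the 7.4 points between ANCOVA and Wilcoxon, 6.1 (96.4 − 90.3) come from dropping the baseline and 1.3 (90.3 − 89.0) from using ranks. The same ANCOVA formula gives 98.1% at ρ = 0.3, 94.2% at 0.7 and 91.7% at 0.9, so the total gap to the Wilcoxon falls to about 3 points at 0.9.

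**Simulated power (%), 4,000 trials per setting, difference 30, SD of change 80.** Rank ANCOVA is Quade's test: residuals of ranked change on ranked baseline, compared by arm.

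| Errors | ρ | Wilcoxon | Rank ANCOVA | Loss |
|---|---|---|---|---|
| Normal | 0.3 | 89.0 | 97.5 | 8.5 |
| Normal | 0.5 | 88.4 | 94.8 | 6.4 |
| Normal | 0.7 | 88.4 | 92.2 | 3.8 |
| Normal | 0.85 | 89.3 | 90.8 | 1.5 |
| t(4) | 0.3 | 92.8 | 99.6 | 6.8 |
| t(4) | 0.5 | 93.8 | 98.6 | 4.8 |
| t(4) | 0.7 | 95.3 | 97.9 | 2.6 |
| t(4) | 0.85 | 95.9 | 97.0 | 1.1 |
| Lognormal | 0.3 | 97.2 | 100 | 2.8 |
| Lognormal | 0.5 | 98.1 | 100 | 1.9 |
| Lognormal | 0.7 | 99.4 | 100 | 0.6 |
| Lognormal | 0.85 | 99.9 | 100 | 0.1 |

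The t(4) losses depend on how the heavy tails are generated. Another set of 3,000 trials per setting gave 4.2, 3.8 and 2.0 points at ρ = 0.3, 0.5 and 0.7. At ρ = 0.5 under no effect, type I error was 4.8% to 5.0% for the Wilcoxon and 5.2% to 5.3% for rank ANCOVA.

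**Disagreement with the ANCOVA verdict.**

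| Errors | ρ | Wilcoxon (%) | Rank ANCOVA (%) |
|---|---|---|---|
| Normal | 0.3 | 9.8 | 1.2 |
| Normal | 0.5 | 8.8 | 2.3 |
| Normal | 0.7 | 7.1 | 3.0 |
| Normal | 0.85 | 4.9 | 3.1 |
| t(4) | 0.3 | 4.8 | 1.6 |
| t(4) | 0.7 | 5.2 | 5.0 |
| t(4) | 0.85 | 6.0 | 5.8 |
| Lognormal | 0.5 | 4.8 | 4.9 |
| Lognormal | 0.7 | 7.0 | 7.1 |

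The normal rows use 4,000 trials and the others 2,500. In the normal rows nearly all the Wilcoxon disagreement is a significant ANCOVA beside a non-significant Wilcoxon (9.5, 8.2, 6.3 and 3.8 points of the totals).

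**The case against.** The strongest reply is that the Wilcoxon is meant for non-normal data, and there it often beats the ANCOVA: 97.1% against 95.5% with t(3) errors and 98.1% against 94.8% with lognormal errors, both at ρ = 0.5. This stands. A reader might infer that the check has less power than the primary analysis when it is needed, but that ordering often reverses once normality fails. The loss that persists is against a baseline-adjusted rank test.

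Second, 432 was sized without baseline adjustment, so the Wilcoxon keeps essentially the design power. This also stands: what is forgone is a gain the plan never counted on.

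Third, a reader might infer that chance baseline imbalance biases the Wilcoxon. At ρ = 0.5 the baseline SD is 80 / √(2 × 0.5) = 80, so a one-SE imbalance is 9.2 and shifts the raw difference in mean change by 0.5 × 9.2 = 4.6. But 9.21² − 7.97² = 21.3, which is about 4.6². The shift is the same efficiency loss expressed another way; it is already in the unadjusted standard error, and type I error is held.

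Fourth, a reader might infer that the check cannot do its job, or that it would settle the trial if normality failed. Neither follows. The test is valid, and the documents call it supportive and give it no decision rule. Under strong skew, or heavy tails with high correlation, adjusting for baseline barely changes how often a rank test and the ANCOVA disagree, because the disagreement then comes mainly from ranking.

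Finally, moving the probability estimate to regression residuals would change the planned quantity and would need an interval method that allows for the fitted slope. That is a good reason to add a test and not to replace this one.

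**Conclusion.** The point holds as a minor one. Among the supportive analyses whose model is stated, the Wilcoxon is the only test of the treatment effect without baseline Zc. Against a baseline-adjusted rank test it gives up about 1.5 to 9 power points with normal data, about 1 to 7 with t(4) errors and 0.1 to 2.8 with lognormal errors. With normal data it also produces avoidable disagreement with the ANCOVA, in about 5% to 10% of trials against about 1% to 4%.

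These sizes rest on assumed correlations of 0.3 to 0.85, equal variances at the two visits, and SD 80 being the SD of change. If 80 were instead the ANCOVA residual SD, Wilcoxon power would be 72.8%, 78.7% and 83.5% at ρ = 0.3, 0.5 and 0.7. The wording of SAP section 3 and the reproduction of 432 as an unadjusted comparison favour the change reading.

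**What to change.** In SAP 2.5.4, add a prespecified Quade rank ANCOVA: rank change in Zc and baseline Zc over both arms, regress ranked change on ranked baseline, and compare the residuals by arm. Name it as the baseline-adjusted nonparametric test to read beside the ANCOVA. Keep the planned Wilcoxon, with its probability estimate and 95% interval on observed change, exactly as specified.

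The cost is a sentence or two in the SAP, one line in section 4 and a little programming. Baseline Zc is already collected, and the sample size and primary analysis do not change. The addition should be made before unblinding; made later, it should be labelled post hoc.
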